### 5.6.6 Evaluation exit

Subjects are exited from the evaluation following the completion of their PCI. There are no follow-up assessments or visits.

### 5.6.7 Withdrawal

Subjects can voluntarily withdraw from the screening process or discontinue the evaluation at any time during their participation, which begins following written informed consent and continues until the completion of their PCI procedure.

The clinical operator can also decide to withdraw a subject from the evaluation if he or she determines that it is in the best interest of the subject to cease participation.

	Title: Vis-Rx Prime Micro-Imaging Catheter Clinical Evaluation Study – Clinical Investigation Plan	Document No. MISC-074
	Page 20 of 28	Revision: C

## 5.7 Procedures

The use of the Gentuity HF-OCT imaging technology in this clinical evaluation is intended to align with the standard-of-care use of other intracoronary imaging technologies, including other available HF-OCT imaging platforms and IVUS as well. Gentuity HF-OCT imaging can be used at various times during the typical PCI procedure to assess or visualize the atherosclerotic lesion or the administered interventional treatment such as a coronary stent. The use of other FDA-cleared intravascular lesion assessment technology, such as Fractional Flow Reserve (FFR) for physiological analysis, is not restricted.

### 5.6.8 HF-OCT Imaging Steps

The steps in the Gentuity HF-OCT imaging procedure include the following:

1. Preparation of the HF-OCT System Console according to the User Manual.
2. Selection of pullback parameters on the HF-OCT System Console. The following are recommended for optimal HF-OCT imaging for this study:
  - a. Pullback length 100 mm
  - b. Flush media: 100% (undiluted) contrast media
3. Preparation of the Vis-Rx Prime Micro-Imaging Catheter according to the Instructions for Use.
4. Preparation of contrast media flush according to the Instructions for Use.
5. Positioning the Vis-Rx Prime lens marker distal to the target lesion in order to acquire an HF-OCT pullback image of the distal landing zone, the target lesion, and the proximal landing zone.
6. Administration of contrast media flush to clear blood from lesion during image acquisition.
7. Initiation of the imaging pullback when blood clearance is obtained and subsequent image acquisition.
8. Post-acquisition image playback and review for lesion assessment and measurements.

Following the PCI procedure, the interventional cardiologist operator will complete the Likert-scale performance assessment to provide product feedback.

## 6 Statistical Analysis Plan

### 6.1 Introduction

The study features a prospective, single arm, unblinded, multi-center design. The study will enroll between 30 and 70 subjects who will undergo HF-OCT imaging at 3-5 participating centers. The objective of this study is to evaluate the clinical and technical performance in the target patient population. The clinical performance will be measured by the operator's subjective evaluations of catheter preparation, catheter deliverability, overall catheter ease of use, and image quality. The technical performance will be measured by an objective measurement of the length of clarity in each HF-OCT pullback or Clear Image Length (CIL, in millimeters).

The Gentuity HF-OCT can capture up to 100 mm of vessel segment in a single pullback. The study's primary hypothesis states that the true population median CIL is greater than the reference standard of

	Title: Vis-Rx Prime Micro-Imaging Catheter Clinical Evaluation Study – Clinical Investigation Plan	Document No. MISC-074
	Page 21 of 28	Revision: C

35 mm, such that a one-sample comparison of median to a reference CIL standard or  $\mu_0$  can be expressed as the following:

$H_0: \mu = \mu_0$  vs.  $H_1: \mu \neq \mu_0$ , where  $\mu_0 = 35$  mm was chosen per the analysis of Section 5.2

The test will be accomplished by a one-sample two-sided exact Wilcoxon signed-rank test with 0.05 type I error rate. The data support  $\mu > \mu_0$  if the two-sided p-value is less than 0.05 and the estimate of  $\mu$  is greater than  $\mu_0$ .

For all enrolled subjects who are included in the Primary Analysis Population, clinical data, and collected HF-OCT images will be retained and analyzed for technical performance. For subjects who were consented and enrolled but who were screening failures during the PCI procedure via lesion-specific exclusion criteria, any clinical data collected prior to PCI will not be included in the evaluation demographic, medical history, or PCI details analyses.

For all enrolled subjects and cases that involve HF-OCT imaging, the clinical operator will be interviewed to evaluate the Gentuity HF-OCT technology for its clinical performance in catheter preparation, catheter deliverability, image quality, and overall performance.

The following sections describe the plans for statistical analysis of the evaluation results. The statistical analysis plan is based on the minimum enrollment into the Primary Analysis Population, which is 30 subjects.

## 6.2 Sample Size Calculation

The study plans to enroll and image at least 30 subjects with the HF-OCT imaging technology, and up to 70 subjects. Conservatively, each participating subject is expected to have an average of 1.3 imaging pullbacks, for an anticipated total of approximately 39 imaging pullbacks (or more) captured with HF-OCT in the evaluation. The number of HF-OCT pullbacks performed in an eligible lesion is according to the discretion of the operator and in consideration of intravascular imaging guidelines. It is therefore expected that this evaluation will collect at least 39 HF-OCT pullback images. For the purpose of power calculation, we assume that 39 HF-OCT pullback images will be obtained from the minimum of 30 subjects. Another reasonable assumption to make in this case is that these 39 pullback images are statistically independent. The argument for statistical independence lies in the fact that CIL is very dependent on the details of the artery shape, the local flow, and the positioning of the guide catheter which delivers the flush. These factors yield a great deal of variability in the resulting CIL measurements even among vessels from the same subject.

The power analysis was performed using SAS/STAT PROC POWER and mean-based paired t-test, while the actual analysis will be median, or rank based due to abnormality in the skewed CIL data distribution. To compensate for the methodology difference, a Wilcoxon adjustment factor was applied. This adjustment factor to the sample size is based on an assumed data distribution. The adjusted sample size  $N_w$  is equal to:  $N_w = N_T / WW$ , where  $N_T$  is the unadjusted sample size using the paired t-test and  $WW$  is the Wilcoxon adjustment factor for the assumed data distribution and has a range between  $2/3$  and  $\pi/3$ . A conservative decision was made to use the adjustment factor resulting in the largest adjusted sample size  $N_w$ .

	Title: Vis-Rx Prime Micro-Imaging Catheter Clinical Evaluation Study – Clinical Investigation Plan	Document No. MISC-074
	Page 22 of 28	Revision: C

The Gentuity HF-OCT technology is designed with a longer, 100 mm pullback length. It is expected that about 20% of the pullbacks will be in the 75 mm range. Setting the expected mean CIL at 45 mm and a target reference CIL of 35 mm (corresponding to an effect size 10 mm), standard deviation of 17 mm, 5% type 1 error rate, a study with 38 vessels will provide more than 80% power for the above hypothesis testing.

**Table 1:** Various effect size, standard deviation, and sample size to attain approximately 80% power.

Effect Size $\Delta = \mu - \mu_0$	SD in $\Delta$	Unadjusted Sample Size ( $N_T$ )	Adjusted Sample Size ( $N_w$ )	Power
6	10	24	36	80.4%
7	12	27	40	81.6%
8	14	27	40	81.5%
9	16	27	40	80.3%
10	17	25	38	80.6%
11	19	26	39	81.0%
12	21	27	40	81.5%

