## 5 Objectives of the Evaluation

The aim of this clinical evaluation is to assess the performance of the Gentuity HF-OCT Imaging System with the Vis-Rx Prime Micro-Imaging Catheter in a real-world setting. The objective is to evaluate the clinical and technical performance in the target patient population.

This evaluation will collect safety and performance data for the system in a real-world clinical setting in patients who are candidates for PCI, including coronary angiography images and HF-OCT imaging both pre- and post-intervention. To objectively evaluate the performance of the Gentuity system, clear image length will be determined by an independent core lab experienced in reading HF-OCT intravascular images. The target median clear image length is based on a meta-analysis of 64 randomized controlled trials that found an average coronary lesion length of  $17 \pm 4$  mm. The target clear image length includes two standard deviations above the average coronary lesion length, plus two 5 mm “landing zones”, one proximal and one distal to the stent, which should provide ample margin to image the full target lesion and demonstrate efficacy of the technology. Further, the performance of the Gentuity HF-OCT products will be rated by clinicians experienced with using other HF-OCT imaging technologies to guide PCI procedures. The evaluation results will be used by Gentuity to prepare for its wider clinical use, and to support further regulatory approvals.

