OCT than there are subjects enrolled in this evaluation. Furthermore, each lesion can be imaged with HF-OCT multiple times throughout the PCI procedure, beginning with pre-intervention to visualize the lesion characteristics, later post-intervention following stent deployment to assess stent expansion and determine if stent struts are well-apposed to the vessel wall, and to determine if further stent expansion is necessary. The number of HF-OCT pullbacks performed in an eligible lesion is at the discretion of the operator and in consideration of intravascular imaging guidelines. It is therefore expected that this evaluation will collect more HF-OCT pullback images than enrolled subjects. This will provide an adequate sample of HF-OCT pullback images for CIL statistical analysis in the target patient population (Section 7.2).

Following the conclusion of each PCI case, the acquired HF-OCT pullback images will be anonymized and transferred to an independent core lab experienced in analysis of clinical intracoronary HF-OCT pullback images. The core lab will analyze each HF-OCT pullback according to pre-determined criteria for image clarity, and each pullback will receive a CIL score.

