## 6.6 Technical Performance Analysis

The clear image length analysis will be conducted on HF-OCT pullbacks acquired in this evaluation by an independent core lab experienced with intracoronary HF-OCT imaging analysis. A clear image frame has at least 270° of visible lumen. CIL is the extent of clear image frames in a given pullback, measured in millimeters. The acquired pullbacks will reflect a range of coronary arteries, atherosclerotic lesions, and procedural timepoints. These factors result in a great deal of variability in the CIL measurements even among pullbacks from the same subject. Consequently, for these CIL data, it is reasonable to utilize statistical methodologies normally suitable only for independent observations. The primary analysis will be performed using SAS/STAT PROC UNIVARIATE and features an exact one-sample two-sided Wilcoxon signed-rank test using “CIL minus 35” as outcome. The data will reject the null hypothesis and support Gentuity HF-OCT’s claim of superiority to the reference standard if the two-sided p-value is less than 0.05 and the median CIL estimate greater than 35 mm.

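### The primary CIL test treats all pullbacks as independent, so its 5% type I error is not assured when a subject contributes more than one pullback

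*Combined protocol and SAP*

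**What the plan says.** Section 6.2 expects an average of 1.3 pullbacks per subject, hence 39 from the minimum of 30 subjects, and adds: "Another reasonable assumption to make in this case is that these 39 pullback images are statistically independent". The reason given is that artery shape, local flow and guide-catheter position make CIL vary a great deal, even among vessels of one subject.

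Section 6.6 uses the same reasoning for the primary analysis. It notes that pullbacks span arteries, lesions and procedural timepoints, and concludes that "it is reasonable to utilize statistical methodologies normally suitable only for independent observations". Every analysable pullback then enters a single test. Section 6.1 specifies it: "The test will be accomplished by a one-sample two-sided exact Wilcoxon signed-rank test with 0.05 type I error rate". Section 6.6 declares success "if the two-sided p-value is less than 0.05 and the median CIL estimate greater than 35 mm".

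Section 5.2 leaves the number of pullbacks to the operator, allows more than one lesion per subject, and says that "each lesion can be imaged with HF-OCT multiple times throughout the PCI procedure". Section 5 says the data will include "HF-OCT imaging both pre- and post-intervention". No maximum is set. No clustered test, subject-level analysis or other sensitivity analysis is planned.

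**The concern.** A signed-rank test takes its null variance from the assumption that each observation is an independent draw. Pullbacks from one subject share that subject, that session and usually the operator, and sometimes the same artery and lesion. High variability within a subject shows that the ICC is below 1; it does not show that it is 0. Section 6.2 also argues from variation among vessels, whereas Section 5.2 allows repeats in the same lesion.

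If the ICC is positive, the variance of the test statistic is larger than the test assumes, so the p-value is too small and 39 overstates the information. The error grows with each additional pullback per subject, while the plan regards extra pullbacks as making the sample adequate. At stake is error control for the primary hypothesis, on which Section 6.6 rests a superiority claim and which is meant to support a European submission (Section 1.1).

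**Working it through.** **Inputs from the documents.** 39 pullbacks from 30 subjects (6.2); reference CIL 35 mm, expected mean 45 mm, so a difference of 10 mm, with "standard deviation of 17 mm, 5% type 1 error rate" (6.2); two-sided signed-rank test at 0.05 (6.1); success also requires a median above 35 mm (6.6).

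**Assumed, because the documents do not give it.** The ICC: 0.2, 0.4 and 0.6 for type I error, and 0.1 to 0.7 for power. The planned layout is taken as 21 subjects with one pullback and 9 with two: 21 + 18 = 39.

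**Step 1: reproduce the plan's figure.** A one-sample t-test with difference 10, SD 17 and N_T = 25 has power 80.56% (noncentral t); Table 1 states 80.6%. Dividing by the least favourable Wilcoxon factor, 25 / (2/3) = 37.5, rounded up to 38, as stated. The calculation is correct if the pullbacks are independent.

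**Step 2: design effect.** With m pullbacks per subject, DE = 1 + (Σm²/Σm − 1) × ICC.
- Planned layout: Σm² = 21×1 + 9×4 = 57 and 57/39 − 1 = 0.4615. DE = 1.09, 1.18, 1.28 at ICC 0.2, 0.4, 0.6. Effective N = 39/DE = 35.7, 32.9, 30.5.
- Two per subject: DE = 1 + ICC = 1.2, 1.4, 1.6.
- Three per subject: DE = 1 + 2×ICC = 1.4, 1.8, 2.2.

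**Step 3: type I error.** Approximation: 2 × [1 − Φ(1.96/√DE)]. Check: 20,000 simulated trials per cell of the signed-rank test (normal approximation), normal data with a subject random effect, true median exactly 35 mm.

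| Layout | Approximation, ICC 0.2 / 0.4 / 0.6 | Simulated |
|---|---|---|
| 39 from 30 (planned) | 6.1 / 7.2 / 8.3% | 5.8 / 7.0 / 8.0% |
| 60 from 30 | 7.4 / 9.8 / 12.1% | 7.1 / 9.3 / 11.9% |
| 90 from 30 | 9.8 / 14.4 / 18.6% | 9.0 / 13.8 / 18.3% |

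A false success needs the upper tail only, nominally 2.5%. In the planned layout it is 2.8 / 3.6 / 4.1%; in the other layouts it is about half the two-sided figure. The exact version of the test, simulated for the planned layout at ICC 0.1 / 0.3 / 0.5 / 0.7, gives two-sided 5.5 / 6.4 / 7.7 / 8.4%, in line with this.

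**Step 4: power on the plan's own scale.** t-test power at (39/DE) × 2/3:

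| ICC | Effective N | Power | Pullbacks needed in place of 38 |
|---|---|---|---|
| 0 | 39.0 | 82.2% | 38 |
| 0.1 | 37.3 | 80.3% | 40 |
| 0.3 | 34.3 | 76.6% | 43 |
| 0.5 | 31.7 | 73.0% | 47 |
| 0.7 | 29.5 | 69.6% | 50 |

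**Step 5: one value per subject, for comparison.** With 30 values and normal data, simulated signed-rank power is about 86%. On the plan's scale, 30 × 2/3 = 20, and the t-test at N_T = 20 has power 70.4%.

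**The case against.** The best defence is that the planned layout is close to one pullback per subject, so little clustering is possible. Pullbacks in different arteries, or before and after stenting, may differ almost as much as pullbacks from different patients. The endpoint is also defined on pullbacks (5.2, 5.4), so a pullback-level analysis is a legitimate choice.

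Much of this stands. At 1.3 per subject the inflation is modest. The documents do not show that the drivers of CIL are mostly shared within a subject; the fair criticism is only that the plan's argument does not establish independence. Moving to one value per subject would change the quantity being estimated. What does not stand is the step from large variability to no correlation, or reliance on 1.3: the plan itself calls that figure conservative and sets no cap.

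Four stronger readings are tempting but not supported:
- **A CIL interval that is too narrow.** None is planned. Section 6.3 lists mean, SD, median and range, and success rests on the p-value and the median.
- **An actual error of 9 to 18%.** That needs three pullbacks per subject as well as the assumed ICCs. Pre- and post-intervention imaging makes two or more plausible, but no document figure says so.
- **Repeats after poor images give some subjects extra weight.** Section 6.8 already excludes pullbacks with a noted procedural error, so this could concern only other repeats.
- **One value per subject keeps 80% power with no more patients.** This holds for normal data, not on the plan's 2/3 scale (Step 5).

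**Conclusion.** The concern holds as a failure to assure the stated error rate. With any positive within-subject correlation, the primary test rejects too often and 39 overstates the effective sample size. For assumed ICCs of 0.2 to 0.6 the effect is modest in the planned layout and becomes serious at two or three pullbacks per subject, which the plan permits. False success is roughly half of each two-sided figure.

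The size rests on an ICC that the documents do not give and on normal data with equal correlation between any two pullbacks of a subject. Skewed CIL data were not simulated; the symmetry that the signed-rank test requires is a separate matter. Power is the lesser issue: with normal data the test as planned keeps simulated power of 91% or more at 39 pullbacks up to ICC 0.7, because the 2/3 factor is cautious.

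**What to change.** 1. In Section 6.6, keep the median CIL over pullbacks as the endpoint and replace the primary test with one that accounts for clustering by subject: a cluster-adjusted signed-rank or sign test, or a bootstrap that resamples subjects. Fix the choice before CIL results are seen.
2. Add a sensitivity analysis with one CIL value per subject, such as the first pullback not excluded under Section 6.8.
3. Delete the independence argument from Sections 6.2 and 6.6.
4. Use one unit throughout the sample-size text, which now refers to 38 vessels in one place and 39 pullbacks in another.
5. Restate effective N and power over a stated ICC range, as in Step 4.

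The cost is SAP wording, some programming, slightly larger p-values and a less favourable stated power. The change of test needs no extra patients. If the sponsor wants 80% on its own scale, 40 to 50 pullbacks at 1.3 per subject means 31 to 39 subjects (40/1.3 = 30.8; 50/1.3 = 38.5), within the planned 30 to 70. If one value per subject were made primary instead, the plan should disclose that 30 subjects give about 86% power for normal data but about 70% on the 2/3 scale, where 38 subjects would be needed for 80%.

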### 6.3 Remarks About Statistical Analysis

All the analyses will be performed using SAS statistical software, version 9.4 or higher, primarily PROC FREQ for categorical data and PROC UNIVARIATE for continuous data. For categorical variables, subject counts and percentages will be generated. For continuous variables, mean, standard deviation, median and range will be generated. Two-sided p-values of less than 0.05 will be considered as statistically significant. Analyses will be based on the observed data only. Missing data will not be imputed. Multiple comparison adjustment will not be performed.

### 6.4 Baseline Analysis

Subject demographic variables will be summarized descriptively. Medical history findings and PCI details will be tabulated. Protocol deviations will be listed.

### 6.5 Clinical Performance Analysis

The performance endpoints consist of the following four previously identified categories (Section 5.1):

- Catheter preparation
- Catheter deliverability
- Image quality
- Overall performance

Subjective criteria within these categories will be evaluated and rated using the 5-point Likert scale by the interventional cardiologist clinical operator. The performance endpoints will be analyzed by mean and standard deviation. As the Likert scale evaluation will be conducted following the PCI case of each enrolled subject, the performance evaluation sample will be equivalent to the number of enrolled

	Title: Vis-Rx Prime Micro-Imaging Catheter Clinical Evaluation Study – Clinical Investigation Plan	Document No. MISC-074
	Page 23 of 28	Revision: C

subjects who underwent HF-OCT imaging. The primary performance objective is to achieve a mean rating of greater than 3 (or acceptable) for the above four categories. No inferential statistical analysis will be performed for these clinical performance endpoints.

Three (3) to five (5) centers will enroll subjects, and there may be multiple interventional cardiologist clinical operators at each participating center. Therefore, there will be a range of clinical operators who evaluate the performance of the Gentuity HF-OCT Imaging System and Vis-Rx Prime Catheter in a range of PCI cases.

## 6.6 Technical Performance Analysis

The clear image length analysis will be conducted on HF-OCT pullbacks acquired in this evaluation by an independent core lab experienced with intracoronary HF-OCT imaging analysis. A clear image frame has at least 270° of visible lumen. CIL is the extent of clear image frames in a given pullback, measured in millimeters. The acquired pullbacks will reflect a range of coronary arteries, atherosclerotic lesions, and procedural timepoints. These factors result in a great deal of variability in the CIL measurements even among pullbacks from the same subject. Consequently, for these CIL data, it is reasonable to utilize statistical methodologies normally suitable only for independent observations. The primary analysis will be performed using SAS/STAT PROC UNIVARIATE and features an exact one-sample two-sided Wilcoxon signed-rank test using “CIL minus 35” as outcome. The data will reject the null hypothesis and support Gentuity HF-OCT’s claim of superiority to the reference standard if the two-sided p-value is less than 0.05 and the median CIL estimate greater than 35 mm.

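### The primary signed-rank test does not hold its stated error rate for the median CIL when CIL is right-skewed, as the plan expects; the size of the excess depends on the shape

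*Combined protocol and SAP*

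**What the plan says.** Section 6.1 says the primary hypothesis "states that the true population median CIL is greater than the reference standard of" 35 mm, and specifies a "one-sample two-sided exact Wilcoxon signed-rank test with 0.05 type I error rate". Section 6.6 says the primary analysis "features an exact one-sample two-sided Wilcoxon signed-rank test", applied to CIL minus 35, and declares success "if the two-sided p-value is less than 0.05 and the median CIL estimate greater than 35 mm".

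Section 6.2 gives the reason for a rank method: "the actual analysis will be median, or rank based due to abnormality in the skewed CIL data distribution". It then describes the expected distribution: "It is expected that about 20% of the pullbacks will be in the 75 mm range", with a mean of 45 mm and an SD of 17 mm.

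The plan nowhere assumes symmetry about the median, transforms CIL, names the pseudomedian as the target, or specifies a sign test or a confidence interval for the median.

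**The concern.** The reason given for the test is the condition under which it stops being a test of the median. The signed-rank test drops normality but keeps symmetry. If CIL has a long right tail, a population whose median is exactly 35 mm does not satisfy the null that the test actually examines, and the error favours a pass.

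This is the study's primary hypothesis and its only planned inferential test; section 6.5 rules out inference on the Likert ratings. It supports a superiority claim against the 35 mm standard, in data intended for a European submission (section 1.1). Because the test is aimed at a different parameter, the excess grows with the number of pullbacks. Enrolment may close anywhere from 30 to 70 subjects.

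**Working it through.** **Inputs.** From section 6.1: reference 35 mm, two-sided 5% (2.5% on the success side). From section 6.2: mean 45 mm, SD 17 mm, about 20% near 75 mm, and 1.3 pullbacks per subject, taken as independent. So 30 × 1.3 = 39 pullbacks at minimum enrolment and 70 × 1.3 = 91 at maximum. The full shape of CIL is not given, so every shape below is an assumption.

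**1. The plan's own figure.** Table 1, row 10/17: noncentrality = (10/17) × √25 = 2.94 on 24 df, which gives power 80.56% (stated 80.6%). Then N_w = 25 / (2/3) = 37.5, rounded up to 38. The row reproduces, so the sample-size arithmetic is not at fault here.

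**2. What the test responds to.** The signed-rank statistic counts the pairwise averages (X_i + X_j)/2, i ≤ j, that exceed 35. It is centred, apart from a term that vanishes with N, when P[(X_1 + X_2)/2 > 35] = 1/2, that is, when the pseudomedian is 35. Median and pseudomedian coincide under symmetry.

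**3. A shape that matches the plan.** Take 80% N(37.5, 8) + 20% N(75, 8).
- Mean = 0.8 × 37.5 + 0.2 × 75 = 45.
- Variance = 8² + 0.8 × 0.2 × 37.5² = 64 + 225 = 289, so SD = 17.
- The median solves 0.8 Φ((m − 37.5)/8) = 0.5, so m = 37.5 + 8 × 0.3186 = 40.05.

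Shifted down to a median of 35, this shape has mean 39.9 and pseudomedian 36.8.

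**4. Pass rate with a true median of exactly 35 mm.** The full rule was simulated with the exact critical value (attainable one-sided size 2.46% at N = 39). There were 100,000 trials per row, except 40,000 for the 5% tail.

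| Assumed CIL shape, median 35 mm | N = 39 | N = 60 | N = 91 |
|---|---|---|---|
| Normal, SD 17 (symmetric) | 2.5% | – | – |
| 5% near 75 mm, rest SD 8 | 3.4% | – | 4.2% |
| 10% near 75 mm, rest SD 10 | 4.9% | 5.8% | 7.3% |
| Lognormal, SD 10 | 5.5% | 6.7% | 8.4% |
| Gamma, SD 17 | 6.2% | 7.7% | 10.1% |
| Lognormal, SD 17 | 7.9% | 10.4% | 14.1% |
| Plan-matched mixture, shifted | 10.1% | 13.9% | 19.3% |
| 20% held at 75 mm, rest N(32.5, 8) | 10.4% | 14.1% | 19.9% |
| Mirrored lognormal, SD 17 (left skew) | 0.7% | 0.4% | 0.2% |

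On the same data the exact sign test passes 1.2% of the time at N = 39, 1.3-1.4% at N = 60 and 1.7-1.8% at N = 91, up to simulation error, whatever the shape.

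**5. The sample-median condition.** In the shifted plan-matched mixture at N = 39, rejection in the favourable direction alone occurs in 10.08% of trials, and rejection with a sample median above 35 mm in 10.07%. Samples that reject upwards almost always meet the second condition, so it removes almost nothing.

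**6. Power of the sign test.** Assume 80% N(37.5, s) with s = 6 to 10, and 20% near 75 mm (mean 45). Then p = P(CIL > 35) = 0.8 Φ(2.5/s) + 0.2, which is 0.729 at s = 6 and 0.679 at s = 10. The smallest count with a binomial tail of at most 2.5% under p = 0.5 gives:

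| Independent pullbacks | Count needed | Power, s = 10 to s = 6 |
|---|---|---|
| 30 | 21 | 49-72% |
| 39 | 27 | 51-76% |
| 70 | 44 | 85-98% |
| 91 | 56 | 92-99% |

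The plan's signed-rank rule under the same mix has 87-97% at N = 39.

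**The case against.** The strongest reply is that the null shape is not in the documents. The 20% near 75 mm describes the device as the sponsor expects it to perform, with mean 45 mm. No section says that a device with a median of 35 mm would keep that tail; with a 5% tail the rate at 39 pullbacks is only 3.4%. The word skewed also names no side. This stands, and it is why the result is a range. It does not remove the problem: the only stated feature of the shape points right, and every right-skewed shape tried exceeds 2.5%.

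A second reply is that the consequence is small. In the shifted mixture the pseudomedian is 36.8 − 35 = 1.8 mm above the median, and under the plan's expectations the median is about 40 mm, where the claim is true. That also stands: the error matters only if the true median is near 35 mm. But a type I error rate is defined at that boundary.

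A reader might infer that the trial has a 10% or 20% false-positive rate. The documents do not support a single figure; those values need the full 20% tail to persist at the null, and the larger one needs 91 pullbacks as well. A reader might also infer that the claim is probably false or that Table 1 is wrong. Neither follows.

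**Conclusion.** The mismatch is real. The claim is about the median, the test is not unless CIL is symmetric, and the plan itself says CIL is not. The stated 5% two-sided error rate therefore does not hold for the stated claim. On the success side the rate is roughly 3.5-10% at 39 pullbacks and 4-20% at 91, against a nominal 2.5%.

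This rests on right skew, which is inferred from the expected tail near 75 mm, on assumed shapes, and on independent pullbacks as the plan assumes. Within-subject correlation is outside these figures. It should be settled before the CIL data are analysed.

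**What to change.** **Lead option.** Keep the signed-rank test. In sections 6.1 and 6.6, restate the hypothesis, estimate and claim as the Hodges-Lehmann pseudomedian with its 95% CI, and let that estimate replace the sample median in the success rule. Report the sample median with a distribution-free 95% CI and no inferential claim on it. This is a wording change and costs no power. The downsides are that the claim no longer concerns the median, so the endpoint wording in sections 1.4, 5, 5.2 and 5.4 must follow, and that under skew the test's level for the pseudomedian is approximate rather than exact.

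**If the claim must stay on the median.** Make the exact sign test of CIL against 35 mm primary, or equivalently require the lower limit of the distribution-free 95% CI for the median to exceed 35 mm. PROC UNIVARIATE, already named, prints the sign test. Keep the signed-rank test as supportive. The cost is power: under the assumed mix it is about 51-76% at the planned 39 pullbacks, so the stated 80% would not hold at minimum enrolment. Section 6.2 would need a restated power and probably a higher minimum; 70 independent pullbacks give about 85-98%.
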